7.0 TRIAL PROCEDURES

7.1 Trial Procedures

The Trial Flow Chart - Section 6.0 summarizes the trial procedures to be performed at each visit. Individual trial procedures are described in detail below. It may be necessary to perform these procedures at unscheduled time points if deemed clinically necessary by the investigator.

Furthermore, additional evaluations/testing may be deemed necessary by the investigator and or the Sponsor for reasons related to subject safety. In some cases, such evaluation/testing may be potentially sensitive in nature (e.g., HIV, Hepatitis C, etc.), and thus local regulations may require that additional informed consent be obtained from the subject. In these cases, such evaluations/testing will be performed in accordance with those regulations.

7.1.1 Administrative Procedures

7.1.1.1 Informed Consent

The investigator or qualified designee must obtain documented consent from each potential subject or each subject's legally acceptable representative prior to participating in a clinical trial or Future Biomedical Research.

7.1.1.1.1 General Informed Consent

Consent must be documented by the subject's dated signature or by the subject's legally acceptable representative's dated signature on a consent form along with the dated signature of the person conducting the consent discussion.

A copy of the signed and dated consent form should be given to the subject before participation in the trial.

The initial informed consent form, any subsequent revised written informed consent form and any written information provided to the subject must receive the IRB/ERC's approval/favorable opinion in advance of use. The subject or his/her legally acceptable representative should be informed in a timely manner if new information becomes available that may be relevant to the subject's willingness to continue participation in the trial. The communication of this information will be provided and documented via a revised consent form or addendum to the original consent form that captures the subject's dated signature or by the subject's legally acceptable representative's dated signature.

Specifics about a trial and the trial population will be added to the consent form template at the protocol level.

The informed consent will adhere to IRB/ERC requirements, applicable laws and regulations and Sponsor requirements.

7.1.1.1.2 Consent and Collection of Specimens for Future Biomedical Research

The investigator or qualified designee will explain the Future Biomedical Research consent to the subject, answer all of his/her questions, and obtain written informed consent before performing any procedure related to Future Biomedical Research. A copy of the informed consent will be given to the subject.

7.1.1.2 Inclusion/Exclusion Criteria

All inclusion and exclusion criteria will be reviewed by the investigator or qualified designee to ensure that the subject qualifies for the trial.

7.1.1.3 Subject Identification Card

All subjects will be given a Subject Identification Card identifying them as participants in a research trial. The card will contain trial site contact information (including direct telephone numbers) to be utilized in the event of an emergency. The investigator or qualified designee will provide the subject with a Subject Identification Card immediately after the subject provides written informed consent.

The subject identification card also contains contact information for the emergency unblinding call center so that a health care provider can obtain information about trial medication/vaccination in emergency situations where the investigator is not available.

7.1.1.4 Medical History

A medical history will be obtained by the investigator or qualified designee. Prior history of acute and chronic GVHD, maximum grade, and dates will be collected.

7.1.1.5 Prior and Concomitant Medications Review

7.1.1.5.1 Prior Medications

The investigator or qualified designee will review prior medication use, including any protocol-specified washout requirement, and record prior medication taken by the subject within 28 days before starting the trial. Treatment for the disease for which the subject has enrolled in the study will be recorded separately and not listed as a prior medication.

7.1.1.5.2 Concomitant Medications

The investigator or qualified designee will record medication, if any, taken by the subject during the trial through the Safety Follow-up visit. In addition, new medications started within 28 days prior to and during the Second Course Phase through the Second Course Safety Follow-up visit should be recorded.

All medications related to reportable SAEs and ECIs should be recorded as defined in Section 7.2.

7.1.1.6 Disease Details and Treatments

7.1.1.6.1 Disease Details

The investigator or qualified designee will obtain prior and current details regarding disease status.

7.1.1.6.2 Prior Treatment Details

The investigator or qualified designee will review all prior cancer treatments including systemic treatments, prior transplantation, radiation, and surgeries and record in the trial database.

7.1.1.6.3 Subsequent Antineoplastic Therapy Status

The investigator or qualified designee will collect transplant parameters (ie. date and type of transplant, conditioning regimen), and will review all new antineoplastic therapy initiated after the last dose of trial treatment. If a subject initiates a new antineoplastic therapy within 30 days after the last dose of trial treatment, the 30 day Safety Follow-up visit must occur before the first dose of the new therapy. Once new antineoplastic therapy has been initiated the subject will move into survival follow-up.

7.1.1.7 Assignment of Screening Number

All consented subjects will be given a unique screening number that will be used to identify the subject for all procedures that occur prior to randomization or allocation. Each subject will be assigned only one screening number. Screening numbers must not be re-used for different subjects.

Any subject who is screened multiple times will retain the original screening number assigned at the initial screening visit.

Specific details on the screening visit requirements (screening/rescreening) are provided in Section 7.1.5.1.

7.1.1.8 Assignment of Randomization Number

All eligible subjects will be allocated, by non-random assignment, and will receive a randomization number. The randomization number identifies the subject for all procedures occurring after treatment allocation. Once a randomization number is assigned to a subject, it can never be re-assigned to another subject.

A single subject cannot be assigned more than 1 randomization number.

7.1.1.9 Trial Compliance (Medication/Diet/Activity/Other)

Interruptions from the protocol specified treatment for 12 weeks between pembrolizumab doses due to toxicity require consultation between the investigator and the Sponsor and written documentation of the collaborative decision on subject management.

Administration of trial medication will be witnessed by the investigator and/or trial staff. The total volume of trial treatment infused will be compared to the total volume prepared to determine compliance with each dose administered.

The instructions for preparing and administering pembrolizumab will be provided in the Pharmacy Manual

7.1.2 Clinical Procedures/Assessments

7.1.2.1 Adverse Event (AE) Monitoring

The investigator or qualified designee will assess each subject to evaluate for potential new or worsening AEs as specified in the Trial Flow Chart and more frequently if clinically indicated. Adverse experiences will be graded and recorded throughout the study and during the follow-up period according to NCI CTCAE Version 4.0 (see Section 12.6). Toxicities will be characterized in terms regarding seriousness, causality, toxicity grading, and action taken with regard to trial treatment.

All AEs of unknown etiology associated with pembrolizumab exposure should be evaluated to determine if it is possibly an event of clinical interest (ECI) of a potentially immunologic etiology (irAE). See Section 5.6.1 regarding the identification, evaluation, and management of AEs of a potential immunological etiology.

Please refer to Section 7.2 for detailed information regarding the assessment and recording of AEs.

7.1.2.2 Physical Exam

7.1.2.2.1 Full Physical Exam

The investigator or qualified designee will perform a complete physical exam during the screening period. Clinically significant abnormal findings should be recorded as medical history. A full physical exam should be performed during screening and repeated as per the frequency defined in the Study Flow Chart. After the first dose of trial treatment new clinically significant abnormal findings should be recorded as AEs.

7.1.2.2.2 Directed Physical Exam

For cycles that do not require a full physical exam per the Trial Flow Chart, the investigator or qualified designee will perform a directed physical exam as clinically indicated prior to

trial treatment administration. New clinically significant abnormal findings should be recorded as AEs.

7.1.2.3 Vital Signs

The investigator or qualified designee will take vital signs at screening, prior to the administration of each dose of trial treatment and at treatment discontinuation as specified in the Trial Flow Chart (Section 6.0). Vital signs should include temperature, pulse, respiratory rate, weight and blood pressure. Height will be measured at screening only.

7.1.2.4 Electrocardiogram

A standard 12-lead ECG will be performed using local standard procedures at screening. Clinically significant abnormal findings should be recorded as medical history.

7.1.2.5 Eastern Cooperative Oncology Group (ECOG) Performance Status

The investigator or qualified designee will assess ECOG status (see Section 12.5) at screening, prior to the administration of each dose of trial treatment and discontinuation of trial treatment as specified in the Trial Flow Chart.

7.1.2.6 Assessment of Disease and Tumor Imaging

7.1.2.6.1 Criteria for Assessment of Disease

1. Anti-tumor activity of pembrolizumab will be evaluated using the following criteria
 - Revised Response Criteria for Malignant Lymphoma. (Cheson et al, *J Clin Oncol*, 2007) [40] See Section 12.7

The International Working Group criteria will be applied by the site as the primary measure for assessment of disease response and as a basis for all protocol guidelines related to disease status (eg, discontinuation of study therapy).

2. Anti-tumor activity of pembrolizumab will also be evaluated by independent central review as part of the exploratory analyses using the following criteria:

5-Point-Scale per the Lugano Classification (Cheson et al, *J Clin Oncol*, 2014) [41] See Section 12.7.1

7.1.2.6.2 Lymphoma Disease Response Assessment

Lymphoma response assessment by CT/PET is based on the International Working Group response criteria for malignant lymphoma (Cheson et al, *J Clin Oncol*, 2007) [41]. Local reading (investigator assessment with site radiology reading) will be used to determine subject eligibility and for subject management. The Sponsor will also receive radiologic images for a retrospective analysis of subject eligibility and treatment response to be

performed by a central vendor. Assessment of lymphoma B symptoms should occur with each lymphoma disease response assessment.

7.1.2.6.3 Disease Assessment of Immunotherapeutic Agents

Immunotherapeutic agents such as pembrolizumab may produce antitumor effects by potentiating endogenous cancer-specific immune responses, which may be functionally anergic. The response patterns seen with such an approach may extend beyond the typical time course of responses seen with cytotoxic agents, and can manifest a clinical response after an initial increase in tumor burden or even the appearance of new lesions. Standard response assessment criteria may not provide a complete response assessment of immunotherapeutic agents such as pembrolizumab. Therefore in the setting where a subject assessment shows PD, study drug may be continued, at the discretion of the PI, until the next disease response assessment provided that the subjects' clinical condition is stable. However, imaging should occur at any time where there is clinical suspicion of progression.

NOTE: With next response assessment if the disease is clinically stable or clinically improved, an exception may be considered to continue treatment upon consultation with the Sponsor.

7.1.2.6.4 Timing of Disease Assessments

Uniform disease response assessments will occur every 12 weeks following the first assessment at Week 12 (see [Table 6](#) below).

Table 6 Disease Response Assessments

Indication	Assessment Frequency
HL (Cohorts 1, 2, and 3)	Every 12 weeks following first assessment at Week 12

7.1.2.6.5 Initial Disease Assessment

Initial disease assessment or tumor imaging must be performed within 28 days prior to the first dose of trial treatment. The site study team must review pre-trial images to confirm the subject has measurable disease as defined in the inclusion criteria.

Disease assessments or scans performed as part of routine clinical management are acceptable for use as the screening scan if they are of diagnostic quality and performed within 28 days prior to the first dose of trial treatment. CT and PET should be used throughout the study at time-points designated in Section 6.0-Flowchart. For lymphomas that are not FDG-avid at screening, PET does not need to be repeated in follow-up assessments.

7.1.2.6.6 Disease Assessments During the Trial

Disease assessments should be performed per the frequency defined above. There is a \pm 7 day window for assessments performed after Day 1. If PET and CT scan at Screening are negative for disease involvement in the neck, subsequent CT scans may not include neck. If PET and CT scans at Screening are positive for disease involvement of the neck, subsequent CT scans must include neck. Following screening, CT scans should be repeated every 12 weeks for subsequent assessments. PET should be repeated at Week 12, Week 24, to confirm CR or PD and as clinically indicated. Disease assessments and imaging should not be delayed for delays in cycle starts.

Disease assessments and imaging should continue to be performed until documented disease progression, the start of new anti-cancer treatment, withdrawal of consent, death, or the end of the study, whichever occurs first.

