7.1.5.4.2 Survival Follow-up

Once a subject experiences confirmed disease progression or starts a new antineoplastic therapy, the subject moves into the survival follow-up phase and should be contacted approximately every 12 weeks to assess for survival status until death, withdrawal of consent, or the end of the study, whichever occurs first.

CCI

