8.6.1.3 Progression-Free Survival (PFS)

The non-parametric Kaplan-Meier method will be used to estimate the PFS curve.

Since disease progression is assessed periodically, progressive disease (PD) can occur any time in the time interval between the last assessment where PD was not documented and the assessment when PD is documented. For the primary analysis, for the subjects who have PD, the true date of disease progression will be approximated by the date of the first assessment at which PD is objectively documented per IWG criteria, regardless of discontinuation of study drug. Death is always considered as a confirmed PD event.

A secondary analysis will be performed for PFS based on investigator's assessment.

In order to evaluate the robustness of the PFS endpoint, we will perform two sensitivity analyses with a different set of censoring rules. The first sensitivity analysis is the same as the primary analysis except that it censors at the last disease assessment without PD when PD or death is documented after more than one missed disease assessment. The second sensitivity analysis is the same as the primary analysis except that it considers initiation of new anticancer treatment to be a PD event for subjects without documented PD or death and lost to follow-up to be a PD event for subjects without documented PD or death and lost to follow-up after ≥ 2 missed disease assessments. The censoring rules for primary and sensitivity analyses are summarized in [Table 12](#).

Table 12 Censoring rules for Primary and Sensitivity Analyses of PFS

Situation	Primary Analysis	Sensitivity Analysis 1	Sensitivity Analysis 2
No PD and no death; new anticancer treatment is not initiated	Censored at last disease assessment	Censored at last disease assessment	Censored at last disease assessment
No PD and no death; subject receives SCT following response to pembrolizumab	Censored at last disease assessment before SCT	Censored at last disease assessment before SCT	Censored at date of SCT
No PD and no death; new anticancer treatment is initiated	Censored at last disease assessment before new anticancer treatment	Censored at last disease assessment before new anticancer treatment	Progressed at date of new anticancer treatment
PD or death documented after ≤ 1 missed disease assessment	Progressed at date of documented PD or death	Progressed at date of documented PD or death	Progressed at date of documented PD or death

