8.6.1.4 Duration of Response (DOR)

Duration of response is defined, only for the subgroup of subjects who achieve CR or PR, as the time from start of the first documentation of objective tumor response (CR or PR) to the first documentation of tumor progression or to death due to any cause, whichever comes first. The analysis will consist of Kaplan-Meier estimates. Duration of response data will be censored on the date of the last disease assessment documenting absence of progressive disease for subjects who do not have tumor progression and are still on study at the time of an analysis, are given antitumor treatment (including stem cell transplant) other than the study treatment, or are removed from study prior to documentation of tumor progression.

Duration of Response will be based upon central review according to the IWG criteria; a secondary analysis of DOR will be conducted using investigator assessment. In addition, since stem cell transplant post-initiation of MK-3475 is considered to be an indicator of positive efficacy rather than failure of the current treatment, an exploratory analysis of DOR may be conducted where date of SCT is not considered censored for those subjects; details will appear in the sSAP.

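### Progression called by the site but not by central review is censored in central-review primary PFS, Sensitivity Analysis 1 and DOR, and only partly recovered in Sensitivity Analysis 2

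*Combined protocol and SAP*

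**What the plan says.** **Who calls progression.** Section 7.1.2.6.1 has the site apply the IWG criteria as the primary measure of response and "as a basis for all protocol guidelines related to disease status (eg, discontinuation of study therapy"). Section 7.1.2.6.2 adds that the local reading "will be used to determine subject eligibility and for subject management".

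**When central review happens.** The same section states: "The Sponsor will also receive radiologic images for a retrospective analysis of subject eligibility and treatment response to be" carried out by a central vendor. Nothing provides for central confirmation of PD before imaging ends.

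**When imaging ends.** Section 7.1.2.6.6: "Disease assessments and imaging should continue to be performed until documented disease progression, the start of new anti-cancer treatment, withdrawal of consent, death" (study closure also ends them). Footnote b of the Section 6.1 flow chart reserves post-treatment imaging for subjects who stop without documented progression. Section 7.1.5.4.2: "Once a subject experiences confirmed disease progression or starts a new antineoplastic therapy, the subject moves into the survival follow-up phase".

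**What is analysed.** Section 8.6.1.3 makes investigator-assessed PFS a secondary analysis, and Table 13 lists central review first. Section 8.6.1.4: "Duration of Response will be based upon central review according to the IWG criteria; a secondary analysis of DOR will be conducted using investigator assessment".

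**How it is censored.** Table 12 has six situations, and none describes site PD without central PD. The first is "No PD and no death; new anticancer treatment is not initiated", which is censored at the last disease assessment in all three columns. Section 8.6.1.4 censors DOR at the last assessment without PD, including when other antitumour treatment is given.

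**The concern.** The reader who stops the scans is not the reader whose dates are analysed. Once the site has settled on PD, the central reader normally receives no later images. If the existing images do not meet central PD, central review cannot date that progression.

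Such a subject leaves the risk set because the treating physician saw progression. If the site's call carries information about imminent central PD, Kaplan-Meier treats the subject as exchangeable with those still being scanned and overstates PFS and DOR. The trial is single-arm, so the curve itself is the result and no comparator offsets the bias. Table 11 lists PFS and DOR as key secondary endpoints.

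**Working it through.** **Step 1: trace the subject through the rules.** The subject has site PD (after any repeat scan) and no central PD.

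| What happens next | Primary PFS | Sensitivity 1 | Sensitivity 2 | Central DOR |
|---|---|---|---|---|
| Alive, no new treatment | Censored | Censored | Censored | Censored |
| Alive, new anticancer treatment | Censored | Censored | Event at treatment start | Censored |
| Alive, lost after ≥2 missed assessments | Censored | Censored | Event at loss | Censored |
| Alive, SCT following response | Censored | Censored | Censored at SCT | Censored |
| Dies, no new treatment | Event | Censored if ≥2 assessments missed | Event | Event |

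The plan gives no discordance rate and no PFS or DOR figure to reproduce, so the size can only be illustrated. Below, *d* is the assumed share of discordant subjects. PFS times are assumed exponential, scans are every 12 weeks (Section 7.1.2.6.4), and one month is 4.345 weeks. No discordant subject dies before central PD.

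**Step 2: size in the primary column.** Assume a 12-month median (52.14 weeks) and a site call one scan before central PD.

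- Per-interval survival: q = exp(−ln 2 × 12/52.14) = 0.8525, so p = 1 − q = 0.1475.
- Complete central reading at 48 weeks: q⁴ = 52.8%.
- No earlier on-study scan exists for PD at the first scan, so that interval keeps hazard p. Later intervals have h = (1−d)p / [(1−d) + dq].
- Primary analysis at 48 weeks: q(1−h)³.

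| d | h | Primary 48-week PFS | Rise (points) |
|---|---|---|---|
| 10% | 0.1347 | 55.2% | 2.4 |
| 20% | 0.1215 | 57.8% | 5.0 |
| 30% | 0.1080 | 60.5% | 7.7 |

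A simulation of 20,000 subjects gave 52.9% with complete reading and 55.3%, 57.8% and 60.8% as planned.

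**Step 3: what Sensitivity Analysis 2 recovers.** Here the site-PD time is exponential with an assumed 9-month median, central PD would come one scan later, and a share *f* of discordant subjects starts new treatment before the next scan. Now q = exp(−ln 2 × 2.762/9) = 0.8084 and p = 0.1916. Four scans fall within 12 months.

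- Central reading with continued scans: q⁴ + d q³ p.
- Primary and Sensitivity 1: [1 − (1−d)p]⁴.
- Sensitivity 2: {[1 − (1−d)p] × q/(q + dfp)}⁴.

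For d = 20%:

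| 12-month PFS | Closed form | Simulation (200,000) |
|---|---|---|
| Central, continued scans | 44.7% | 44.9% |
| Primary and Sensitivity 1 | 51.4% | 51.5% |
| Sensitivity 2, f = 0 | 51.4% | 51.5% |
| Sensitivity 2, f = 50% | 46.8% | 46.9% |
| Sensitivity 2, f = 80% | 44.3% | 44.4% |
| Sensitivity 2, f = 100% (equals site reading) | 42.7% | 42.8% |

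Across medians of 5.6 to 14 months and d of 10-30%, the same formulas put primary 12-month PFS 2.6 to 11.8 points above central reading with continued scans. The lowest figure is for a 14-month median and 10% (61.3% against 58.7%). The highest is for 5.6 months and 30% (40.4% against 28.6%).

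**The case against.** Three stronger statements are tempting, and the documents support none of them.

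- *These subjects are censored in both sensitivity analyses.* Not in general. Sensitivity Analysis 2 counts new anticancer treatment and loss to follow-up after at least two missed assessments as events. Death is an event in the primary analysis and in Sensitivity Analysis 2.
- *Imaging stops at the first site call.* Section 7.1.2.6.7 provides repeat imaging 4-6 weeks later for clinically stable subjects. If PD is not confirmed and treatment continues, the 12-week schedule resumes. Section 7.1.2.6.3 and footnotes n and o of Section 6.1 also allow further images. Central review will therefore sometimes see another scan. Clinically unstable subjects need no repeat scan, and confirmation is still the site's.
- *No planned analysis could reveal the problem.* Investigator-read PFS and DOR are planned and count every site PD as an event. A gap between the two readings would be a signal. But that analysis changes the reader for every subject, so the gap mixes reader disagreement with informative censoring.

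It is also fair to say that a mistaken site call, unrelated to later progression, would cause no bias, and that Section 8.3 plans no hypothesis test for PFS or DOR. Both points limit the weight of the concern. Neither supplies the missing Table 12 row, and DOR has no dedicated sensitivity analysis for this case.

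**Conclusion.** The gap is real but bounded. Central-review primary PFS, Sensitivity Analysis 1 and DOR censor living subjects with site PD and no central PD. Sensitivity Analysis 2 recovers them only so far as they die, start new treatment or are lost after repeated missed assessments, and it dates the event then, not at site PD. The expected direction is upward.

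The 2-8 point figure applies to the primary column at 48 weeks with a 12-month median. It rests on an assumed 10-30% discordance, a fixed one-scan lag, and no repeat scan that would let central review call PD. It is an illustration, not an estimate for this trial. The residual in Sensitivity Analysis 2 runs from the whole bias (no one starts new therapy) to none (most do). DOR is the more exposed endpoint, because other antitumour treatment is censored there too. The argument does not touch the ORR test, which is not a time-to-event analysis. This is a change worth making, not a flaw in the primary result.

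**What to change.** 1. Add a row to Table 12: *No central PD and no death; treatment or scheduled imaging ended because of investigator-assessed progression.* Keep it censored in the primary analysis and Sensitivity Analysis 1. In Sensitivity Analysis 2, count it as progressed at the date of investigator-assessed PD.
2. State that this row takes precedence over the new-anticancer-treatment and lost-to-follow-up rows when investigator PD comes first. Otherwise one subject meets two rows with different event dates. The same sentence should say how the row ranks against the SCT row.
3. Add to Section 8.6.1.4 one sensitivity analysis of central-review DOR that applies the same rule.
4. Report the number of discordant subjects per cohort.

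The cost is one row, two or three sentences and one count. Investigator PD dates are already needed for the planned investigator-read PFS. Trial conduct and the primary analysis do not change. The downside is a less favourable sensitivity estimate.
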